11.4 Treatment Procedures

11.4.1 Patient Number Assignment and Randomization

Patients will be assigned a study ID number serially once they have signed the CMV consent form or main study consent form if the CMV consent form is not required, this number will stay with them as they are checked for study eligibility. This number should be referenced on all patient-specific study-related material. A permuted-block randomization scheme developed by the study biostatistician will be used to assign patients to treatment arms. The randomization module for the Duke electronic database system (Title 21 CFR Part 11 Compliant) will be used for this purpose.

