	
Beginning with protocol version 20181218, patients who are MGMT unmethylated will only receive one adjuvant cycle of the TMZ regimen according to their assigned randomized arm. Patients who are MGMT methylated or whose methylation status is inconclusive will continue with up to 12 cycles of TMZ. All patients enrolled prior to approval of protocol version 20181218 will receive 6-12 cycles of TMZ, independent of their MGMT methylation status. Patients who are dependent on steroid supplements above immune suppressive levels (4 mg) at time of vaccination or who are unable to tolerate TMZ will be withdrawn from the study and replaced before vaccination.
 
Up to 70 patients may be consented on the main informed consent to meet the goal of 26 evaluable patients (13 per arm) for the primary outcomes.
 
For both arms, the patients must be screened at Duke within 3 ± 1 weeks after the completion of standard of care radiation. For both arms, the initial cycle of adjuvant TMZ will begin as soon as possible following randomization. For Arm 1, the adjuvant TMZ cycle(s) will be given at a standard targeted dose of 150-200 mg/m²/d for 5 days. For Arm 2, the adjuvant TMZ cycle(s) will be at the dose-intensified dose of 75-100 mg/m²/d for 21 days. If a patient enrolls after approval of protocol version 20181218 and has an MGMT unmethylated tumor, they will discontinue TMZ after the 1st cycle.
 
All patients will have blood drawn for immune monitoring and then receive a tetanus pre-conditioning injection intradermally (i.d.) in the RIGHT groin (as described below) on day 22 (+1 day) of cycle 1 of adjuvant TMZ. On the following day, the patients will receive study vaccine. The vaccine is administered as follows: 500 µg of PEP-CMV Component A mixed with Montanide ISA-51 administered i.d. with half on the right groin and half on the left groin. Vaccines #2 and #3 will be given at 2 week (+ 3 days) intervals; the MRI visit with immune monitoring will take place within 2 weeks (+3 days) of vaccine #3. Prior to the 20181218 amendment, vaccination consisted of two components: Component A and Component B. However, after that amendment, vaccination for all newly enrolled patients consisted of Component A only.
 
For patients enrolled before approval of protocol version 20181218 and for patients enrolled after approval of protocol version 20181218 who have an MGMT methylated tumor or MGMT methylation status in inconclusive, TMZ cycle 2 will begin after that visit, but no sooner than 14 days post vaccine 3. This will result in at least ~35-day delay before starting TMZ cycle 2. MGMT unmethylated patients enrolled after approval of protocol version 20181218 will not receive subsequent cycles of TMZ, but will continue to receive vaccines approximately every 4 (+2) weeks.
 
An unacceptable toxicity will be defined as any \geq Grade 3 toxicity possibly, probably, or definitely related to the PEP-CMV vaccine with the following exceptions. A portion of the Grade 3 vaccine reactions noted in prior patient experiences with the PEP-CMV vaccine, described in Sections 11.5.1 and 14.2.1, will not be considered unacceptable if they are indicative of immune response. That is, toxicities such as Grade 3 flu-like symptoms, fever, and chills/rigors will not be considered unacceptable toxicities if the duration is less than 72 hours. Any \geq Grade 3 organ toxicity (cardiac, renal, hepatic), including CRS-related toxicities such as hypotension and

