11 INVESTIGATIONAL PLAN

11.1 Overview

If their CMV serostatus is unknown, patients will consent to CMV screening either prior to or following XRT/TMZ. Patients are enrolled to the study following XRT/TMZ and prior to initiation of post-XRT cycles of TMZ provided they meet all other eligibility criteria (if CMV status is not already known, a screening consent will be obtained for CMV screen only to confirm eligibility). After signing main consent, patients receive a Tetanus-diphtheria booster vaccination with 0.5 mL of Td (tetanus, diphtheria toxoid, adsorbed) intramuscularly. After meeting all eligibility criteria, patients are randomized to one of two arms:

- Arm 1) will receive standard TMZ (150-200 mg/m²/day on days 1-5 of each 28-day cycle).
- Arm 2 will receive dose-intensified TMZ (75-100 mg/m²/day on days 1-21 of each 28-day cycle).

New patients who enroll on study after protocol version 20181218 is approved and who are MGMT unmethylated will only receive one adjuvant cycle of their assigned TMZ regimen. Patients who enroll on study before protocol version 20181218 is approved or enroll on study after protocol version 20181218 is approved and either are MGMT-methylated or their methylation status is inconclusive will continue with up to 12 cycles of TMZ.

MGMT gene promoter methylation status is obtained at Duke using validated testing from LabCorp by PCR and/or from Caris by pyrosequencing. If MGMT gene promoter methylation status has already been conducted outside of Duke, the results will be used, as long as the testing was performed by a validated method/test. If the results of testing by LabCorp, Caris, or other external, validated test is indeterminate or if the results of more than one type of testing are in disagreement, the results will be considered methylated and the patient will be treated per protocol as methylated based on their randomization. That is, Arm 1 will receive standard adjuvant dosing of temozolomide for the first 5 days of each cycle for 6 to 12 cycles. Arm 2 will receive dose-intensified temozolomide for 21 days of each cycle for 6 to 12 cycles.

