11.4.2 PEP-CMV Vaccination

As described above, patients will be randomized to one of two arms (1:1) to receive: (1) standard TMZ (150-200 mg/m²/day on days 1-5 of each 28-day cycle), or (2) dose-intensified TMZ (75-100 mg/m²/day on days 1-21 of each 28-day cycle).

During the first cycle of adjuvant TMZ, all patients will receive a tetanus pre-conditioning injection in the RIGHT groin on Day 22 (+1 day) and the following day receive the vaccine. Previously, patients received vaccine prepared as follows: 500 µg of PEP-CMV Component A mixed with Montanide ISA-51 i.d. administered in the RIGHT groin and 2 hours later, 500 µg of PEP-CMV Component B mixed in 150 µg of GM-CSF i.d. administered in the LEFT groin. With revisions made in protocol v. 20181218, all newly enrolled patients will have the vaccine prepared as follows: 500 µg of PEP-CMV Component A mixed with Montanide ISA-51 administered i.d. with half in the RIGHT groin and half in the LEFT groin. With the 20190318 amendment, Component B will be removed from the vaccination regimen for all patients previously receiving Component B as part of the regimen. The subsequent 2 vaccines will be administered every 2 weeks (+ 3 days) for a total of 3 vaccines. This will result in a ~35-day delay in the second cycle of TMZ. MGMT unmethylated patients, after protocol version 20181218 is approved, will not receive subsequent cycles of TMZ, but will continue to receive vaccines approximately every 4 (+2) weeks.

Patients will be vaccinated in conjunction with subsequent TMZ cycles every 4 (+2) weeks for a total of 6 to 12 cycles of TMZ after RT. Additional vaccines may be administered up to 20 vaccines, at the discretion of the treating neuro-oncologist. All vaccines will be given i.d. approximately 10 cm below the inguinal ligament bilaterally. For MGMT unmethylated patients after protocol version 20181218 is approved, only one cycle of TMZ will be provided; however, vaccines will continue every 4 (+ 2) weeks after the single TMZ cycle for a maximum of 20 (unless tumor progression occurs).

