15.4.3 Exploratory Immunologic Analyses

The following immunologic analyses will focus on patients who are evaluable for the immunologic monitoring primary analysis, i.e., patients who had immunologic monitoring conducted at baseline and prior to the second cycle of TMZ. These analyses will focus primarily upon patients who received only Component A. However, additional analyses may be conducted besides those described below.

Quality of Immune Response: The quality of the immune response will be assessed by polyfunctional flow cytometry. The analysis used here for polyfunctionality will be one that has been successful at distinguishing HIV progressors and non-progressors based on T-cell phenotype [115, 116]. All data will be background subtracted. For each measure, a lower threshold corresponding to two standard deviations above background is set to 0 based on a Poisson model essentially allowing T-cells to be designated as positive or negative for a certain phenotypic marker. The number of positive phenotypic markers post-vaccination will be calculated for each patient. The Kruskal-Wallis test will be used to compare treatment arms with respect to the number of phenotypic markers observed post-vaccination 3, as well as at vaccination 6. Additional exploratory analyses will be conducted using a Fisher's exact test that will compare treatment groups with respect to the proportion of patients with 5 positive markers, and 4 or more positive markers. Analyses similar to those described for the primary immunologic analyses will be used to examine the percentage of tetramer positive cells.

Analysis of covariance will be used to compare treatment groups with respect to the change between baseline and post-vaccination time-points in mean proliferative response and cytokine production, with baseline levels included in the model as a covariate. If assumptions of normality are not satisfied, the Kruskal-Wallis test will be used to compare treatment arms. Analyses will focus on the change between baseline and post-vaccination 3 assessments, as well as the change between baseline and vaccine 6.

Effect on Tregs: The mean levels of Tregs at baseline and at each follow-up assessment will be estimated within each treatment group. A mixed model that accounts for the correlation of repeated measurements within a patient will be used to compare treatment groups with respect to changes in Treg levels over time.

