15.4.4 Other Exploratory Analyses

Progression-Free Survival and Overall Survival: The Kaplan-Meier estimator will be used to describe the progression-free survival (PFS) and overall survival (OS) experience of patients in each treatment group. These analyses will focus on those patients who have received at least 3 vaccines. PFS is defined as the time between the third vaccine and first documentation of death or disease progression/recurrence. Patients remaining alive without disease progression will have PFS censored at their last follow-up. OS is defined as time between the third vaccine and death. It should be noted that these analyses will focus on only those patients who received Component A alone as we have with other analyses. Additional analyses will describe OS and PFS from randomization.

Radiographic Response: Among the subset of patients with residual disease, the proportion of patients with radiographic response will be estimated with 95% confidence interval.

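### From version 20181218 MGMT status decides whether the randomised TMZ schedule continues after cycle 1, but the exploratory post-cycle-1 arm analyses take no account of it

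*Combined protocol and SAP*

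**What the plan says.** - **The rule.** The Synopsis states: "Beginning with protocol version 20181218, patients who are MGMT unmethylated will only receive one adjuvant cycle of the TMZ regimen". The other group differs: "Patients who are MGMT methylated or whose methylation status is inconclusive will continue with up to 12 cycles of TMZ". Section 11.1 repeats the rule and treats an indeterminate or discordant result as methylated. Patients enrolled before that version continue TMZ whatever their status.
- **When MGMT is known.** Section 11.1 says "MGMT gene promoter methylation status is obtained at Duke using validated testing from LabCorp by PCR and/or from Caris by pyrosequencing", and accepts validated outside results. Table 3 lists it in the post-XRT/TMZ screening column, the same column as randomisation.
- **Allocation.** Section 11.4.1: "A permuted-block randomization scheme developed by the study biostatistician will be used to assign patients to treatment arms". Allocation is 1:1 (section 11.4.2). No stratification factor is named.
- **Analyses after cycle 1.** Section 15.4.3 plans a Kruskal-Wallis comparison of arms on the number of phenotypic markers after vaccine 3 and at vaccine 6. It also plans an ANCOVA with the baseline level as its only covariate: "Analyses will focus on the change between baseline and post-vaccination 3 assessments, as well as the change between baseline and vaccine 6". A mixed model compares arms on Treg change over time. Section 15.4.4 adds: "The Kaplan-Meier estimator will be used to describe the progression-free survival (PFS) and overall survival (OS) experience of patients in each treatment group". MGMT appears nowhere in section 15.4.

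**The concern.** The randomised factor is the TMZ schedule. After cycle 1 only the methylated or inconclusive patients still receive it; the unmethylated patients in both arms are off TMZ. A single arm estimate at vaccine 6, or for the later Treg values, thus averages two treatment contrasts, and section 15.4 does not say which question that average answers.

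The protocol's rationale is vaccination during recovery from TMZ-induced lymphopenia, and section 9.5 reports lymphopenia that differs by schedule. Whether TMZ continues is therefore relevant to these readouts. Section 9.5 also ties the survival benefit of TMZ to methylation, so a chance MGMT imbalance between two small arms could be taken for a schedule effect. What is at stake is how the later exploratory results are read, and how much precision they have.

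**Working it through.** **1. The plan's own figure.** Section 15.2 states 81% power with 13 evaluable patients per arm (one-tailed Wilcoxon, type I error 0.025) for the primary ELISPOT comparison. It cannot be reproduced exactly, because only medians and ranges of the ACT II titres are given. Nine invented data sets matching those summaries gave 38% to over 99%, one of them 80%. The figure is possible and is not disputed. No power is stated for vaccine 6, so about 80% serves below only as a benchmark.

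**2. Scheduled exposure by vaccine 6.** Vaccines 1 to 3 fall in the extended cycle 1, then one per cycle, so vaccine 6 falls in cycle 4.
- Continuing patients: 4 × 5 = 20 TMZ days in Arm 1, and 4 × 21 = 84 in Arm 2.
- Unmethylated patients: 5 and 21 days, all in cycle 1.

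**3. Chance imbalance.** Assume allocation not stratified by MGMT, 13 per arm, unmethylated share u (not in the documents). The two arm counts are independent Binomial(13, u).
- u = 50%: difference of 3 or more patients, 0.327; 4 or more, 0.169.
- u = 40% or 60%: 0.317 and 0.160.
- The expected difference is 0. At u = 50% the SD of the difference in proportions is √(2 × 0.5 × 0.5/13) = 0.196.
- Per 1 SD of MGMT effect, an imbalance of 3 shifts the arm difference by 3/13 = 0.23 SD; an imbalance of 4 shifts it by 4/13 = 0.31 SD.

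**4. Type I error.** With no arm effect, an assumed MGMT effect of 0.5 to 1 SD and u = 50%, the simulated unadjusted Wilcoxon test rejects in 0.021 to 0.022 of trials (nominal 0.025). Among the 8-9% of trials with an imbalance of 4 or more in the adverse direction, it rejects in 0.05 to 0.09.

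**5. Dilution.** Let c be the share of the later arm effect that one-cycle patients keep (also not in the documents). The pooled effect is f = (1 − u) + u·c of the full effect. For 81% power at 13 per arm, one-sided 0.025, the standardised signal is 1.960 + 0.878 = 2.838 (effect 2.838 × √(2/13) = 1.11 SD). Power is Φ(2.838·f − 1.960).

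| u | f, c = 0 | power | f, c = 0.5 | power |
|---|---|---|---|---|
| 40% | 0.60 | 40% | 0.80 | 62% |
| 50% | 0.50 | 29% | 0.75 | 57% |
| 60% | 0.40 | 21% | 0.70 | 51% |

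A Wilcoxon simulation with a 1.19 SD effect (79% undiluted) gave 33%, 24% and 16% for c = 0, and 58% falling to 47-48% for c = 0.5. Together: about 16-40% and 47-62%.

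**6. What adjustment does.**
- *MGMT as a main effect.* It does not cure dilution: at u = 40%, c = 0 and no MGMT shift, linear-model power goes from 36% to 38%. It does recover precision: with an assumed 1 SD MGMT effect and a constant arm effect, power rises from about 74% to 81%. It also returns the rejection rate under an adverse 4-patient imbalance to 0.025 or less.
- *Contrast within continuing patients.* It keeps the full effect on (1 − u) of the patients, so its signal is 2.838 × √(1 − u). At u = 40% the factor is √0.6 = 0.775, against a pooled f of 0.60 (c = 0) or 0.80 (c = 0.5). Power is Φ(2.838 × 0.775 − 1.960) = 59% by this approximation and 57% by simulation, against 36% pooled in that simulation, when c = 0. When c = 0.5 there is no power gain; the benefit is a clear question.

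**The case against.** **Arguments that stand.**
- A reader might infer that the arm contrasts are confounded by MGMT. The documents do not support that. MGMT is a baseline factor, the stopping rule is the same in both arms and allocation is randomised, so imbalance is zero in expectation and overall type I error holds (step 4). Comparing assigned strategies, MGMT rule included, is a legitimate randomised comparison, subject to losses before vaccine 6 that might differ by MGMT.
- The most severe power figures assume that one cycle leaves no later effect. Cycle 1 differs by arm for everyone and vaccines 1 to 3 follow it, so some carry-over is plausible.
- A stratified rank test would not help with dilution: simulated power was 34%, 22% and 15%, against 33%, 23% and 17% unstratified (u = 40%, 50%, 60%; c = 0).
- PFS and OS are described without a test in section 15.4.4, so there is no survival test to be biased. The Synopsis and section 11.1 nevertheless speak of clinical endpoint comparisons, and that wording should be reconciled with 15.4.4.
- The plan is not wholly silent on adjustment: the HLA analyses may adjust for confounders, which are not named. Nor does it ignore discontinuation: sections 13.3 and 15.1 allow for patients not receiving TMZ.
- Section 11.4.1 names no stratum; it does not state that the scheme is unstratified.

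**The primary endpoint.** A reader might also infer that the primary comparison is affected. Section 15.4.1 requires an assessment after vaccine 3 and before the second cycle, which precedes the MGMT rule. Section 15.2 takes the peak from blood drawn under the treatment plan, which includes later draws. The documents do not say that those draws count towards the peak, so no such claim is made here.

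**Conclusion.** The point holds as one of precision and interpretation. The vaccine 6 tests, the Treg model and the survival curves ignore a screening variable that determines whether patients remain on the randomised schedule. They average two exposure contrasts, and small arms leave room for chance imbalance: 3 or more patients in 33% of randomisations and 4 or more in 17%, if half are unmethylated and allocation is not stratified.

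The size of the dilution rests on the unmethylated share and the effect kept after one cycle, neither of which is in the documents. Over the ranges shown it runs from moderate to large; if the one-cycle effect persists in full there is none. The priority is minor, because every contrast named is exploratory.

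**What to change.** Leave the randomisation as it is.

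- **15.4.3, covariate.** Add MGMT group (unmethylated versus methylated or inconclusive) to the vaccine 6 ANCOVA and the Treg mixed model. This deals with imbalance and precision.
- **15.4.3, dilution.** Because a main effect does not remove it, also give the arm contrast at vaccine 6 and for later Treg values within each MGMT group, or through an arm-by-MGMT term, labelled exploratory.
- **15.4.4.** Report arm-by-MGMT counts, and show PFS and OS by arm within MGMT group as description.

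The cost is a few lines in section 15.4, using data already collected at screening. The downsides are small subgroups with wide intervals and the loss of one or two degrees of freedom. Fixing the choice before the later data are analysed avoids a post hoc decision.

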11.4.2 PEP-CMV Vaccination

As described above, patients will be randomized to one of two arms (1:1) to receive: (1) standard TMZ (150-200 mg/m²/day on days 1-5 of each 28-day cycle), or (2) dose-intensified TMZ (75-100 mg/m²/day on days 1-21 of each 28-day cycle).

During the first cycle of adjuvant TMZ, all patients will receive a tetanus pre-conditioning injection in the RIGHT groin on Day 22 (+1 day) and the following day receive the vaccine. Previously, patients received vaccine prepared as follows: 500 µg of PEP-CMV Component A mixed with Montanide ISA-51 i.d. administered in the RIGHT groin and 2 hours later, 500 µg of PEP-CMV Component B mixed in 150 µg of GM-CSF i.d. administered in the LEFT groin. With revisions made in protocol v. 20181218, all newly enrolled patients will have the vaccine prepared as follows: 500 µg of PEP-CMV Component A mixed with Montanide ISA-51 administered i.d. with half in the RIGHT groin and half in the LEFT groin. With the 20190318 amendment, Component B will be removed from the vaccination regimen for all patients previously receiving Component B as part of the regimen. The subsequent 2 vaccines will be administered every 2 weeks (+ 3 days) for a total of 3 vaccines. This will result in a ~35-day delay in the second cycle of TMZ. MGMT unmethylated patients, after protocol version 20181218 is approved, will not receive subsequent cycles of TMZ, but will continue to receive vaccines approximately every 4 (+2) weeks.

Patients will be vaccinated in conjunction with subsequent TMZ cycles every 4 (+2) weeks for a total of 6 to 12 cycles of TMZ after RT. Additional vaccines may be administered up to 20 vaccines, at the discretion of the treating neuro-oncologist. All vaccines will be given i.d. approximately 10 cm below the inguinal ligament bilaterally. For MGMT unmethylated patients after protocol version 20181218 is approved, only one cycle of TMZ will be provided; however, vaccines will continue every 4 (+ 2) weeks after the single TMZ cycle for a maximum of 20 (unless tumor progression occurs).

PEP-CMV is administered as Component A alone (500 μ L per side). As described above, vaccines will be delivered intradermally. Details of the procedure will be recorded on the appropriate eCRF. Patients will receive their 1st vaccine in the OTC with an IV bolus of normal saline prior to vaccination, and the IV saline lock will remain in place in case quick administration of fluids or medications is needed for a reaction. Patients will be pre-medicated with Zofran® and Tylenol® and optionally with oral prednisone at the discretion of the patient and his/her provider if patient has previously experienced post-vaccine reaction(s). Patients will be monitored in the clinic for approximately 4 hours post-immunization for the development of any adverse reactions after vaccines #1 and #2 for a total of 8 sets of vital signs (i.e., every 30 minutes). Supportive medications for post-vaccine reactions may include the following by IV: normal saline bolus, Benadryl, Solumedrol. If no reaction(s) occur during vaccines #1 and #2, patients will be monitored for 2 hours for a total of 4 sets of vital signs (i.e., every 30 minutes) after vaccine #3, as long as the reason for no reactions is not pre-medication with oral prednisone. If no reaction(s) occur after vaccine #3, patients will be monitored for 30 minutes with one set of vital signs for subsequent vaccines, as long as the reason for no reactions is not pre-medication with oral prednisone. If a patient experiences a post-vaccine reaction at any point, the monitoring period will revert to 4 hours until such time as he/she have 2 consecutive vaccines with no reaction. The PI or sub-investigator may extend monitoring periods at any given visit if they feel it is clinically indicated for the patient's safety. Patients who have experienced a significant post-vaccine reaction at any previous vaccine (i.e., \geq Grade 2 toxicity considered possibly, probably, or definitely related to the study vaccine), but who are not removed from study, will receive a bolus of normal saline by IV before study vaccine and the saline lock will remain in place as a precautionary measure. Patients who have never experienced a post-vaccine reaction or only experienced a Grade 1 toxicity with earlier vaccines will not be required to have an IV saline lock placed prior to administration of subsequent vaccines, although the treating provider may opt to proceed with this precautionary measure. The immunization procedures will be supervised by a nurse or physician that has completed Basic Life Support (BLS) course. A cardiac resuscitation cart will be available in the vicinity when performing these immunizations in case of severe allergic reactions.

11.4.3 Treatment Plan for Study Drug Safety Arm (not applicable for patients enrolled on protocol version 6/12/18 or later)

[figure not shown]

Figure 12: Study Drug Safety Arm Study Schema for Vaccine #1.

[figure not shown]

Figure 13: Study Drug Safety Arm Study Schema for Vaccine #2 if the Patient Experiences No Hypersensitivity Reaction to Vaccine #1.

Following the safety events that were initially reported on 4/10/17, 6 additional patients were consented to receive study vaccine with standard of care (SOC) 5-day TMZ at 150-200 mg/m²/d for 28-day cycles. These patients were not randomized according to the original study design to either 21 day or 5-day Temodar; they received only SOC 5 day Temodar cycles. Of these 6 patients, 3 patients were assigned to Schedule A and 3 patients were assigned to Schedule B. They were assigned to Schedule A or B such that every other patient that receives vaccine is on a different schedule, i.e., patient 1 received Schedule A, patient 2 received Schedule B, patient 3 received Schedule A, etc. There was a planned interval of at least 48 hours between each individual patient receiving study vaccine.

Vaccine #1 was administered according to the schematic shown in [Figure 12](#). Every patient received a tetanus preconditioning injection in the RIGHT groin on Day 22 (+1 day) of the TMZ cycle, and the following day received a single component of the vaccine. Component A consisted of 500 µg of PEP-CMV mixed with Montanide ISA-51 i.d. administered in the RIGHT groin and Component B consists of 500 µg of PEP-CMV, gB conjugated to KLH, mixed in 150 µg of GM-CSF i.d. in the LEFT groin. Patients assigned to Schedule A were infused with only Component A at the first vaccine. Patients assigned to Schedule B were infused with only Component B at the first vaccine. Blood for immune monitoring (~ 20 mL³) was drawn just prior to component administration, 1 hour, and 2 hours after component administration. If no hypersensitivity reaction was observed after the administration of only a single Component, the patient received both components at the subsequent vaccine administration, according to [Figure 13](#). If a hypersensitivity reaction occurred in 2 out of 3 Schedule A patients after receiving only Component A, further administration of Component A would be stopped and the study team would evaluate potential modifications for Component A. If a hypersensitivity reaction occurred in 2 out of 3 Schedule B patients after receiving only Component B, but no hypersensitivity reactions had been experienced by Schedule A patients receiving only Component A, further administration of Component B to Schedule B patients would be stopped and all remaining vaccinations would be done with Component A alone. If 2 out of 3 patients on both Schedule A and B experienced hypersensitivity reactions after Vaccine #1, the study team would evaluate potential modifications to both components and no patient would proceed to Vaccine #2.

Those patients who received Vaccine #1 with no hypersensitivity reaction proceeded to Vaccine #2, administered according to [Figure 13](#). Patients assigned to Schedule A had Component A administered in the RIGHT groin and were observed for 2 hours (up to 4 hours), followed by administration of Component B in the LEFT groin. Patients had to be asymptomatic for at least 2 hours before proceeding to administration of Component B. Blood draws occurred every hour, beginning at just prior to Component A administration and ending at the 2 hour observation time point following Component B administration. Blood (~ 20 mL³) was drawn to monitor immune activity through analysis of, but not limited to, TNF α , GM-CSF, IFN α , IFN γ , IL-6, and IL-1. Patients assigned to Schedule B had Component B administered in the LEFT groin and were observed for 2 hours (up to 4 hours), followed by administration of Component A administered in the RIGHT groin. Blood draws occurred every hour, beginning at just prior to Component B administration and ending at the 2-hour observation time point following Component A administration. These 6 patients would continue to receive study vaccine according to their assigned schedule, if

³ One 10 mL EDTA tube, most frequently lavender top for plasma collection, such as BD-36643. One 10 mL serum tube, most frequently red top for serum collection, such as BD-VT6430.

no hypersensitivity reactions occurred, for as long as they remained on study. If patients in Schedule A experienced a hypersensitivity reaction after Vaccine #2, they would continue all further injections according to Vaccine #1, Component A only. If patients in Schedule B experienced a hypersensitivity reaction after Vaccine #2, but there was no hypersensitivity reactions to Schedule A patients with Component A alone, they would continue all further injections with Component A only. After completing Vaccine #2, the immune monitoring blood draws and MRIs followed the schedule described in [Table 3](#) and did not include the additional immune monitoring blood draws that were drawn in Vaccine #1 and Vaccine #2 ([Figure 12](#) and [Figure 13](#)). The timing of the first 3 vaccines could result in a potential ~35-day delay in the second cycle of TMZ.

Patients were vaccinated in conjunction with subsequent TMZ cycles every 4 (+2) weeks for a total of 6 to 12 cycles of TMZ after RT at the discretion of the treating neuro-oncologist. All vaccines were given i.d. approximately 10 cm below the inguinal ligament bilaterally (Component A in the RIGHT groin and Component B in the LEFT). Vaccines continued 4 (+ 2) weeks after TMZ cycles for a maximum of 20 (unless tumor progression occurred).

PEP-CMV was administered as two components, Component A in a total volume of 1 mL and Component B in a total volume of 800 μ L, as described above, that was delivered intradermally. Patients were pre-medicated with Zofran® and were monitored in the clinic for 2 hours post-immunization for the development of any adverse effects. Vital signs were obtained every 15 minutes until discharge from the clinic. Additional follow-up with the patients was done by phone at 24 and 48 hours to inquire about additional symptoms/adverse events experienced in the 48 hours following vaccine. Vaccine administration was supervised by a nurse or physician that has completed Basic Life Support (BLS) course. A cardiac resuscitation cart was available in the vicinity when performing these immunizations in case of severe allergic reactions.

